9.8.1.2. Continuation of Treatment Beyond Radiographic Progression

In the event of radiographic progression per RECIST v1.1 but in the absence of clinical deterioration, worsening ECOG performance status, or disease progression that may compromise organ function, the subject may continue to receive study treatment with AG-120 at the discretion of the treating physician in consultation with the Sponsor Medical Monitor. If there is clinical deterioration or continued radiographic progression documented on subsequent imaging, treatment will be discontinued and the subject will complete the EOT and Follow-up Visits, and enter survival follow-up.

9.8.1.3. Palliative Radiotherapy After Unblinding After Disease Progression

Palliative radiotherapy to treat symptomatic pre-existing or new non-target lesions (per RECIST v1.1) that cannot otherwise be medically managed will be permitted after disease progression has been confirmed and unblinding has occurred. AG-120 should be held for the duration of palliative radiotherapy. A 2-week washout from completion of radiotherapy will be required prior to starting or resuming AG-120. For subjects randomized to placebo who receive palliative radiotherapy before crossing over to AG-120, a repeat CT or MRI will be performed upon completion of the 2-week washout period to document the area that was irradiated and to serve as the new baseline against which all subsequent RECIST v1.1 assessments will be performed,

for the purpose of documenting PFS2 during the unblinded open-label cross over period (see Section 12.12.1). For subjects permitted to continue on open-label AG-120 beyond documented radiographic progression, a new baseline imaging assessment will not be required and the imaging assessments will continue on the current schedule. All decisions to pursue palliative radiotherapy will require Medical Monitor approval.

9.8.1.4. Biliary Tract Obstruction During Treatment

In the event of the development of obstructive jaundice due to biliary tract obstruction, the appropriate measures will be taken to diagnose and relieve the obstruction. Study treatment interruption is not required, but will be permitted at the discretion of the Investigator.

9.9. Guidelines for Management of QT Prolongation

The discussion of the emergency management of Torsades de pointes and its hemodynamic consequences is beyond the scope of this guideline.

Events of QTcF prolongation \geq Grade 2 should be reported as AEs of special interest (AESIs) to the Sponsor within 24 hours, according to expedited reporting procedures (see Section 11.2.3).

The following are guidelines for the management of AEs of special interest based on the AG-120 non-clinical and clinical safety findings in subjects with solid tumors to date.

Prolongation of QTcF interval has been observed in monkeys at relatively high doses of AG-120 (see Section 5.3.2.2) and has been identified as an expected risk of treatment with AG-120 (see the Investigator's Brochure). As of 16 January 2016, 12 (10%) of 122 subjects in Study AG120-C-002 and 19 (16%) of 119 subjects in Study AG120-C-001 have experienced QT prolongation while receiving AG-120.

Subjects may be at increased risk for the development of QT prolongation when treated with AG-120 in combination with fluoroquinolones, azole antifungal agents, or serotonin (5-HT₃) antagonists. Investigators need to be vigilant; refrain from administering concomitant medications associated with QT prolongation and if no other therapeutic options are available, monitor subjects receiving study treatment with the combination of these drugs, and evaluate ECG and electrolytes (including potassium, magnesium, and calcium) particularly in subjects presenting with nausea, vomiting, or diarrhea. Systemic administration of a moderate or strong CYP3A4 inhibitor requires careful monitoring of QTcF (see Section 9.13.2).

Subjects who experience prolongation of the QTcF interval to >480 msec (CTCAE Grade ≥ 2) while receiving study treatment, should be promptly evaluated for causality of the QTcF prolongation and managed according to the following guidelines and Table 2:

- Levels of electrolytes (potassium, calcium, and magnesium) should be checked and supplementation given to correct any values outside the normal range.
- Concomitant therapies should be reviewed and adjusted as appropriate for medications with known QT prolonging effects.
- If no other cause is identified and the Investigator believes it is appropriate, particularly if QTcF remains elevated (after above measures have been implemented, or as determined by the Investigator), study treatment may be interrupted, and an ECG should be rechecked in approximately 1 week after the QTcF prolongation was

first observed or more frequently as clinically indicated. If QTcF has recovered or improved and the Investigator believes it is safe to do so, re-challenge with study treatment should be considered if held.

- ECGs should be conducted at least weekly (eg, at every scheduled visit) for 2 weeks following QTcF reduction ≤ 480 msec.

Table 2: Management of QT Prolongation by CTCAE Grade

CTCAE Grade	Management
Grade 2 (QTcF >480 and ≤ 500 msec)	
 • The dose of study treatment may be reduced to 250 mg QD without interruption of dosing. The dose of study treatment may be re-escalated to the prior dose in ≥ 14 days after QT prolongation has decreased to \leq Grade 1.
Grade 3 (QTcF >500 msec on at least two separate ECGs)	
 • Hospitalization for continuous cardiac monitoring and evaluation by a cardiologist should both be considered. • Dosing with study treatment will be interrupted. If QTcF returns to within 30 msec of baseline or <450 msec for males and <470 msec for females within 14 days, treatment may be resumed at a reduced dose of 250 mg. • The dose of study treatment cannot be re-escalated following dose reduction for Grade 3 QTcF prolongation unless the prolongation was associated with an electrolyte abnormality or concomitant medication.
Grade 4 (QTcF >500 msec or >60 msec change from baseline with Torsades de pointes or polymorphic ventricular tachycardia or signs/symptoms of serious arrhythmia)	
 • Subjects should be admitted to a hospital for continuous cardiac monitoring and discharged only after review by a cardiologist. • Dosing with study treatment should be permanently discontinued.

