8.5.1. Withdrawal from Study Treatment

Subjects may discontinue or be discontinued from study treatment at any time. In this situation, a subject without documented progressive disease by the Investigator should be followed for tumor

assessments until the development of progressive disease and/or survival. Subjects will be discontinued from study treatment for the following reasons:

- Withdrawal of consent
- Certain adverse events (as described in Section 9.8) including instances of Grade 4 QTcF prolongation
- A confirmed diagnosis of PML (Section 11.3.1) or Guillain-Barre syndrome (Section 11.3.2)
- Disease progression (subjects who are, in the opinion of the Investigator, benefitting from treatment [eg, slow progression] may be allowed to continue on study treatment with approval of the Medical Monitor)
- Death
- Investigator decision
- Subject decision to withdraw from treatment (subject may continue with PFS and/or survival follow-up)
- Protocol violation: non-adherence to study treatment regimen or protocol requirements
- Confirmed pregnancy (study therapy should be immediately interrupted based upon a positive urinary human chorionic gonadotropin [hCG] test, and permanently discontinued if confirmed by a serum β -hCG test)
- Lost to follow-up

All AEs should be followed until resolution or for a period of 28 days from the last dose of study treatment, whichever is shorter. If the subject withdrew from treatment because of an AE, every effort must be made to perform protocol-specified safety follow-up procedures.

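### Section 9.9 gives two different restart criteria after Grade 3 QTcF prolongation and does not say which one governs

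*Protocol*

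**What the plan says.** Protocol Section 9.9 defines its scope by a single cut-off, "Subjects who experience prolongation of the QTcF interval to >480 msec" on treatment, which it equates with CTCAE Grade 2 or higher. Such subjects are to be "managed according to the following guidelines and Table 2".

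The third bullet of those guidelines opens with two conditions: "If no other cause is identified and the Investigator believes it is appropriate, particularly if QTcF remains elevated". If they are met, "study treatment may be interrupted, and an ECG should be rechecked in approximately 1 week after the QTcF prolongation was" first seen. The bullet then turns to restarting. If QTcF has recovered or improved, and the Investigator considers it safe, "re-challenge with study treatment should be considered if held". No grade is named.

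Table 2 sets rules by grade:

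- Grade 2 allows a dose reduction without a pause.
- Grade 3 says "Dosing with study treatment will be interrupted". Treatment may resume at 250 mg if, within 14 days, QTcF is back within 30 msec of baseline or below 450 msec (men) or 470 msec (women). Later re-escalation is barred unless an electrolyte abnormality or a concomitant drug was involved.
- Grade 4 says "Dosing with study treatment should be permanently discontinued".

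Section 8.5.1 lists among the reasons for discontinuing treatment: "Certain adverse events (as described in Section 9.8) including instances of Grade 4 QTcF prolongation". The footnote to Table 1 in Section 9.8.1.1 refers readers to Table 2 for dose changes in QTcF prolongation.

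**The concern.** The bullets and the table are joined by a plain conjunction, and Section 9.9 has no sentence giving either of them precedence. The bullet attaches to every event above 480 msec, so on its face it reaches Grades 3 and 4, where the table is stricter.

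QT prolongation is the only expected risk that Section 5.4 names for solid tumours, and the only adverse event of special interest in Section 11.2.3. If an Investigator restarts a Grade 3 subject because QTcF has come down somewhat, the bullet offers protocol text in support, although Table 2's limit has not been met. Whether that restart was a deviation would then be open to dispute.

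There is a smaller consequence for reporting. SAP Section 9.1 tabulates adverse events leading to drug held, reduced and discontinued, and SAP Section 7.6 summarises dose intensity. For QT events, these summaries depend partly on which restart text a site applied.

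**Working it through.** The plan states no figure to reproduce on this point. The check sets the two texts side by side, grade by grade.

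| Grade | Third bullet of Section 9.9 | Table 2 | Result |
|---|---|---|---|
| 2 | Pause optional, re-challenge to be considered | Reduction optional, no pause needed | No conflict; both are permissive |
| 3, pausing | Optional, and only if no other cause is found | Mandatory, no exception for cause | Bullet is looser; pausing satisfies both |
| 3, restarting | QTcF recovered or improved and Investigator considers it safe; no limit, window or dose | Numeric limit, 14-day window, 250 mg | Criteria differ |
| 4 | No exclusion from re-challenge | Permanent stop, with Section 8.5.1 in support | Bullet is looser; the stop is stated twice |

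**Can the two Grade 3 restart criteria give different answers for one subject?** Take a subject with 510 msec on two ECGs, which is Grade 3, whose dosing is paused and whose QTcF then falls to 480 msec. Assume a baseline below 450 msec, as exclusion criterion 15 requires unless the Medical Monitor approves otherwise.

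- Bullet: 510 − 480 = 30 msec lower, so QTcF has improved. If the Investigator considers it safe, re-challenge is to be considered.
- Table 2, relative limit: being within 30 msec of baseline at 480 msec needs a baseline of at least 480 − 30 = 450 msec. A baseline below 450 msec fails.
- Table 2, absolute limit: 480 msec is below neither 450 msec (men) nor 470 msec (women). It fails for both.

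The bullet's criterion is met and Table 2's is not. The criteria also separate on time, because Table 2 speaks only of recovery within 14 days and the bullet has no window. They separate on dose as well, because Table 2 names the resumption dose and the bullet names none. The only QTcF value in the bullets themselves, 480 msec in the fourth, sets how often ECGs are repeated and is not a restart rule.

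**Does the table cover every case in its scope?** Not as worded. Grade 2 ends at 500 msec, Grade 3 needs two ECGs above 500 msec, and Grade 4 needs an arrhythmia or its signs or symptoms. A single reading above 500 msec without arrhythmia fits no row, so only the bullets address it. This is another reason to state where the third bullet applies.

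**How many subjects?** Section 9.9 reports QT prolongation in 12 of 122 solid-tumour subjects, 12/122 = 9.8%. Applied to the 124 planned AG-120 subjects, 0.098 × 124 = 12.2, or about 12. That figure is for any grade and is pooled over doses; Section 7.3 says 84 of the 122 received 500 mg. The documents give no share at Grade 3 or above, and nothing on how many of those subjects would be restarted differently under the two texts. The number affected therefore cannot be derived.

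**The case against.** The strongest reply is that the texts are cumulative. The bullet is permissive: it never tells a site to continue dosing or to restart, so a site that follows Table 2 breaches nothing. The Table 1 footnote points to Table 2, and the layout is a general bullet followed by a grade-specific table. Section 9.8.1.1 asks that dose delays and modifications be discussed with the Medical Monitor beforehand, and Grade 2 or worse events reach the sponsor within 24 hours.

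Most of this stands, and it rules out several stronger readings that a reader might infer:

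- That sites are bound by two incompatible rules at once. They are not; following Table 2 satisfies both.
- That a site could keep dosing through Grade 3 and still comply. It could not. An optional pause in the bullet does not cancel the mandatory one in the table.
- That a cause such as low potassium waives the Grade 3 pause. In that case the bullet's condition is not met and the bullet is silent, while the table's row still applies. Table 2 lets an identified cause affect re-escalation only.
- That Grade 4 subjects may be re-challenged. Table 2 and Section 8.5.1 both provide for discontinuation.
- That the conflict covers every QTcF above 480 msec. Grade 2 has none.

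The reply does not dispose of the Grade 3 restart. There Table 2 grants a conditional permission, and the bullet grants a second one on easier terms. The Table 1 footnote sits in Section 9.8 and does not mention the Section 9.9 bullets. The bullet does require the Investigator to consider restarting safe, but that is a judgment with no stated limit. Discussion with the Medical Monitor and prompt reporting make unnoticed divergence less likely; they do not settle which criterion applies.

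**Conclusion.** The inconsistency is real but narrow. For Grade 3, Section 9.9 contains two restart criteria that can give opposite answers for the same subject, and it does not say which governs. At Grades 3 and 4 the bullet's wording on interruption and re-challenge is also looser than Table 2, although at Grade 4 the other provisions leave little practical doubt.

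The severity is moderate. The matter concerns restarting drug after the principal known risk, which is why it should be corrected. The number of subjects is unknown and likely small, since only Grade 3 or higher events are touched and the roughly 12 expected any-grade events in the AG-120 arm assume that the earlier pooled rate carries over. Sample size, power and type I error are unaffected. The conclusion rests on reading the bullet as written, without an implied grade limit. Which restart rule is clinically right is not judged here.

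**What to change.** Reconcile the third bullet of Section 9.9 with Table 2 and Section 8.5.1. The text should state two things:

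- the grade or grades to which the bullet's interruption and re-challenge wording applies;
- which text governs where the bullet and Table 2 differ.

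In the same edit, say which provision covers a single reading above 500 msec without arrhythmia. The sponsor's medical team decides the clinical content; the requirement is one restart rule per grade.

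The cost is a few words in the next amendment and a letter to sites. No procedures, subjects or analyses are added.

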Treatment Period and End of Treatment Visit: Subjects who meet all study eligibility criteria will be randomly assigned in a 2:1 ratio to receive AG-120 orally at a dose of 500 mg QD or AG-120-matched oral placebo QD. Randomization will be stratified by number of prior systemic therapies (1 vs 2). Daily study treatment will begin on C1D1. Cycles are 28 days (+/-2 days) in duration and dosing is continuous. All subjects will continue to receive best supportive care according to institutional practice throughout the study, regardless of treatment arm. Study visits will be conducted every other week during Cycles 1-3 (Days 1 and 15), and Day 1 of each cycle thereafter. An End of Treatment (EOT) Visit will be performed on the last day of study treatment (within 5 to 33 days of last dose, to accommodate for potential dosing delays of up to 28 days).

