Assessment	ECG	Blood	ECG ²	Blood	ECG ²	Blood	ECG ²	Blood	ECG ²	Blood	ECG ²	ECG
Pre-dose ³	X	X	X			X	X	X ⁴				
Post-dose												
Anytime								X	X	X	X	X
0.5 hr ⁵		X				X						
2 hr ⁵		X	X ⁶	X	X ⁶	X	X ⁶					
4 hr ⁵		X				X						

Abbreviations: D = day, ECG = electrocardiogram, EOT = end of treatment, F/U = follow-up.

Note: All 12-lead ECGs are to be conducted after 3 minutes of recumbency or semi-recumbency. A 12-lead single ECG should also be obtained as clinically indicated.

* The same schedule should be used for placebo subjects who cross over to AG-120 after documented disease progression or Sponsor unblinding of the study.

¹ Assessments to be conducted on the last day of study treatment (within 5 days of last dose of study drug).

² 12-lead ECGs are to be obtained at Day 1 of Cycles 1 and 2, and on C1D15. ECGs should be done before PK sampling on these days. An ECG will be collected on C3D1 and on Day 1 of all cycles thereafter. ECGs are to be obtained within ± 15 minutes of specified time.

³ To be obtained within 30 minutes before dose; can be done any time during Screening.

⁴ Blood samples to be collected at Cycle 3 and beyond, until EOT.

⁵ Blood samples to be obtained within ± 10 minutes of specified time. Blood samples to be collected within 10 minutes after completion of the ECG.

⁶ ECG to be obtained within ± 15 minutes of specified time.

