11.2.3. Adverse Events of Special Interest

An AESI can be serious or nonserious and is an event of special interest to the Sponsor. Ongoing monitoring and rapid communication (within 24 hours) by the Investigator to the Sponsor is required to allow for further characterization and reporting to regulatory authorities.

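### Section 9.9 asks for at least weekly ECGs for 2 weeks after QTcF recovers, but the scheduled visits it offers as an example are 14 or 28 days apart

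*Protocol*

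**What the plan says.** Protocol Section 9.9 covers subjects whose QTcF rises above 480 msec (CTCAE Grade 2 or worse). They are to be "managed according to the following guidelines and Table 2", so the bulleted guidance and the table apply together. The last bullet sets follow-up after recovery: "ECGs should be conducted at least weekly (eg, at every scheduled visit) for 2 weeks following QTcF reduction" to 480 msec or below.

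The Grade 2 row of Table 2 (QTcF above 480 and up to 500 msec) allows a reduction to 250 mg without interruption. It then states: "The dose of study treatment may be re-escalated to the prior dose", once at least 14 days have passed since the prolongation fell to Grade 1 or lower. The row names no ECG.

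Section 7.1 places study visits "every other week during Cycles 1-3 (Days 1 and 15), and Day 1 of each cycle thereafter". Cycles last 28 days, ±2 days. Footnote 2 to Table 4 (Section 10.1) gives the routine ECG schedule: "12-lead ECGs are to be obtained at Day 1 of Cycles 1 and 2, and on C1D15", and "An ECG will be collected on C3D1 and on Day 1 of all cycles thereafter". No ECG is scheduled at C2D15 or C3D15.

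**The concern.** The bullet sets a weekly minimum and then tells sites that ECGs at scheduled visits are one way to meet it. No two scheduled treatment visits are a week apart, so a site that takes the example at face value falls short of the rule.

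The timing makes this more than untidy wording. Grade 2 begins above 480 msec, so falling to Grade 1 or lower in Table 2 is the same event as QTcF falling to 480 msec or below in the bullet. The two weeks of ECG follow-up are therefore the same two weeks that must pass before a Grade 2 subject can go back from 250 mg to 500 mg. A site relying on the example could ask for re-escalation with one ECG since recovery, or none.

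Section 5.4 names QT prolongation as the only expected risk of AG-120 in patients with solid tumors. Section 9.9 reports it in 12 of 122 subjects (10%) in one Phase 1 study and 19 of 119 (16%) in the other. The documents do not say how many of these were Grade 2, so the number of subjects this could affect cannot be estimated.

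**Working it through.** The check is a calendar count.

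**Inputs**
- Required: gaps of at most 7 days for 14 days after recovery, so about 14 / 7 = 2 ECGs (Section 9.9).
- Visits, with C1D1 as day 1: days 1, 15, 29, 43, 57, 71, 85, then every 28 days (Section 7.1).
- Routine ECGs: days 1, 15, 29, 57, 85, then every 28 days; none on day 43 (C2D15) or day 71 (C3D15) (Table 4).
- Visit window: ±2 days.

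**Step 1: gaps between visits.** Nominal gaps are 14 days up to C4D1 and 28 days after it. If one visit is 2 days late and the next 2 days early, the smallest gaps are 14 − 4 = 10 and 28 − 4 = 24 days. Both exceed 7.

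**Step 2: visits in the 14 days after recovery.** For recovery on day d, count the scheduled days v with d < v ≤ d + 14.

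| Recovery day | Scheduled visits | Routine Table 4 ECGs |
|---|---|---|
| Cycles 1-3 (d = 1 to 84) | 1 on 84 of 84 days | 1 on 56 of 84; 0 on 28 of 84 |
| A 28-day cycle from Cycle 4 (d = 85 to 112) | 0 on 14 of 28; 1 on 14 of 28 | 0 on 14 of 28; 1 on 14 of 28 |

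The 28 days in Cycles 1-3 with no routine ECG are d = 29 to 42 and d = 57 to 70, that is, recovery on days 1-14 of Cycle 2 or Cycle 3. From Cycle 4 the next visit after day 85 is day 113. For d = 85 to 98 the period ends by day 112 and holds no visit; for d = 99 to 112 it holds one.

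**Step 3: is there a visit in each week?** A visit in both (d, d + 7] and (d + 7, d + 14] occurs for 0 of 84 and 0 of 28 recovery days.

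**Step 4: can the windows help?** Two visits fit in one 14-day period only if they are 10 to 13 days apart. Take each visit as independent and uniform over −2 to +2 days. A gap shortened by k days then gives k qualifying recovery days, and k = 1, 2, 3, 4 has probability 4/25, 3/25, 2/25, 1/25. The expected number per pair is (4 + 6 + 6 + 4)/25 = 0.8 days. Five neighbouring pairs are relevant in Cycles 1-3 (days 15 to 85), so 5 × 0.8 / 84 = 4.8% of recovery days; a simulation with 40,000 draws gave 4.7%. From Cycle 4 the figure is 0%. Even in the favourable cases the visits are at least 10 days apart, so they are not weekly.

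**The case against.** The strongest reply is that the weekly minimum is the operative rule and an example cannot lower it. A site has to pass over the words directly before the bracket to go wrong. That is correct, and the counts above apply only to a site that leans on the example or on the routine schedule.

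The Grade 2 row also need not repeat a bullet that already applies to it. Recovery can only be established by ECG. There are other controls as well:
- Grade 2 or worse events "should be reported as AEs of special interest (AESIs) to the Sponsor within 24 hours", and for such events "Ongoing monitoring and rapid communication (within 24 hours) by the Investigator to the Sponsor is required".
- Section 9.8.1.1 expects dose decisions to be discussed with the Medical Monitor beforehand and makes re-escalation subject to that person's approval.
- Table 4 allows extra ECGs when clinically indicated.

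All of this stands and limits the consequence. None of it says which ECGs must be available at re-escalation. The footnote to Table 1 sends readers to Table 2 for QTcF, and Table 2 mentions neither the approval nor the ECGs. Its Grade 3 row, by contrast, gives explicit QTcF values for resuming treatment.

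Section 9.9 also asks for a recheck about a week after prolongation is first seen when treatment may be interrupted. This shows that off-schedule ECGs are already expected, but it runs from the onset of prolongation, not from recovery.

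Two points about the counts are fair. Calendar days are not equally likely recovery days, since recovery is recognised only when an ECG is taken; the counts describe the schedule and are not probabilities. They also leave out the ECG that documents recovery. If that is taken at a Cycle 1-3 visit, the next visit is at day 14 with nothing in between. If it is taken at a Day 1 visit from Cycle 4, the next is at day 28. Finally, the Table 4 counts do not test the example itself, which would put an ECG at C2D15 and C3D15; they show only that the routine schedule does not fill the gap.

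**Conclusion.** The concern holds. On nominal dates the example gives one of the roughly two ECGs required in Cycles 1-3, and none or one from Cycle 4. It never gives weekly spacing, with or without the visit windows. That conclusion needs only the 14- and 28-day spacing; the figure of about 5% also assumes independent visit dates spread uniformly over their windows.

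The severity is minor to moderate. The governing rule is adequate, a site that follows it obtains the ECGs, and no efficacy endpoint is affected. It should still be corrected, because it is a wrong instruction within a safety rule for the drug's one named expected risk in this population, and it covers the two weeks before a possible dose increase.

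**What to change.** - In Section 9.9, delete the bracketed example and state that unscheduled ECGs between visits will usually be needed. Keep the weekly frequency.
- In the Grade 2 row of Table 2, add that re-escalation requires the Section 9.9 weekly ECGs to be on file with the most recent QTcF still at or below 480 msec, in addition to the Medical Monitor approval in Section 9.8.1.1.

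This is one deletion, one sentence and one clause, and it adds no ECG beyond those the weekly minimum already requires. Sites will have to book ECGs outside routine visits. The Table 2 clause creates one explicit precondition, and so one new possible deviation. As a protocol change it needs IRB/IEC approval (Section 13.5) across about 55 centers, so it is best included in the next amendment. Deleting the example corrects the error by itself; the Table 2 clause puts the requirement where the dosing decision is made.
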